9.4.5 Medication Accountability

All study medication bottles will be collected/returned from the participant to the study team. When a bottle is returned, a study team member will count how many capsules or left and record the number on the bottle, date and initials. All medication bottles will be returned to the Research Pharmacy for drug accountability. The Research Pharmacy will be asked to sign off on the accountability log showing the bottle is returned. The Research Pharmacy will dispose of medication and bottles.

10 Deep Phenotyping Visits

A subset of study participants (n=160) be offered optional deep phenotyping. These participants will have a separate assessment appointment with study personnel at the CPFRC. There will be two visits that take place after T2-before Treatment 1 and after T3-before Treatment 2. At the deep phenotyping study visit, participants will undergo QST, Structural and functional brain neuroimaging, inflammatory markers assessment and the assessment autonomic functioning.

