10.2 Magnetic Resonance Imaging

All participants will also undergo spinal MRI to assess structural abnormalities of lower back (see Section 6.6 for imaging on all participants). Additionally, a subset of participants enrolled in the deep phenotyping study will undergo four different brain neuroimaging procedures (Figure 10): 1) functional connectivity MRI (fcMRI) at rest, 2) proton magnetic resonance spectroscopy (¹H-MRS) of the posterior insula assessing combined glutamate and glutamine (Glx), 3) evoked pressure pain at a neutral site, and 4) voxel based morphometry to assess gray matter volume in S1 and primary motor (M1) cortex. Following physical maneuvers to exacerbate clinical pain, resting state fcMRI and ¹H-MRS scans will be repeated to assess the neurobiological response to increases in pain, as we have previously demonstrated in FM using pressure.¹³⁹ The methods described below have been successfully employed previously by our group, and probe different aspects of the brain's involvement in pain processing, thus complementing our QST methods by providing a comprehensive neurobiological signature of cLBP. Familiarization procedures will be completed prior to MRI to reduce anxiety. Neuroimaging will require approximately 90 minutes to complete. MRI will be done on a 3 Tesla scanner either at the Functional MRI Lab on UM North Campus (GE scanner) or in the Department of Radiology at the UM

Figure 10 Deep Phenotyping fMRI Breakdown

Main Hospital (Philips scanner).

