Best model selection. We will select best models using the unbiased Bayesian Information Criterion (BIC) and use 10-fold cross-validation to protect against overfitting the model. To deal with potentially high-dimensional phenotype variables and other demographic and clinical covariates, regularized regressions will be considered. Penalties in the likelihood function will follow the Elastic Nets family with LASSO favored for its feature elimination potential. Alternative machine-learning model-free algorithms (random forests, SVMs) will be utilized for comparison, using the binary form of the response variables.

Characterizing the predictive performance. Cross-validated and BIC-based measures of explained variation will be used to characterize the predictive potential of the continuous response models. This analysis will be supplemented with ROC analysis based on the binary form of the response variables. We will use the cross-validated and kernel-smoothed area under the ROC curve (AUC) as an appealing measure of the predictive potential with good interpretability. Order effects will be considered during secondary analysis.

Causal analysis. We will conduct exploratory analysis of causal relationships between the light and deep phenotypic factors and the analgesic and secondary response variables. We are interested in particular causal analyses potentially implicating neurobiological and inflammatory biomarkers (deep phenotyping variables) as having a mechanistic role in the mediation of the treatment effects of light phenotypic measures. Specifically, we will measure the potential mediation effect of the deep phenotype biomarkers as the proportion of the treatment effect (PTE) explained by the biomarker. PTE is represented by a relative change in the treatment regression coefficients when the biomarker is included in the model relative to the coefficient before inclusion. We will use bootstrap methods to estimate standard errors for the proportion of explained treatment effects. Wald test statistic of the form (change in regression coefficient)/(bootstrap Standard Error) will be used to test for the presence of the mediation effect.

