18.2.2 Preliminary Analysis of NPC Data

Prior to the primary analysis (primary treatment outcome will be *PROMIS Pain Interference*) descriptive statistics will be used to characterize the NPC measures, including aspects of data quality. Summary statistics for all key variables will be produced. All data will be passed to the Informatics Core, that need to be combined with self-report and behavioral measures from the BPC (assessing treatment response), for multivariate analyses and building of predictive models. The NPC will also identify high priority variables based on preliminary analyses. For instance, network-whole brain connections associated with pain subtypes (high centralized pain) that meet family-wise statistical correction or stimulated inflammatory markers/QST metrics that show robust associations with clinical characteristics, will be noted. The NPC will also help identify neurobiological markers that are supported by previous work (e.g., DMN-insula connectivity).

We will also conduct exploratory analyses to examine the mechanism of action of specific treatments. Changes in connectivity, QST, inflammatory and ANS patterns following each of the phase 1 treatments will be performed using paired sample t-tests.

We will measure the potential mediation effect of biomarkers (e.g., QST, inflammatory markers, fMRI measures) as the proportion of the treatment effect explained by the biomarker (change in the treatment regression coefficients when the biomarker is included in the model). For all models, we will use appropriate interaction terms to model effect modification. We will use bootstrap methods to estimate standard errors for the proportion of explained treatment effects, and Wald tests to evaluate the mechanistic (mediation) effect. Handling of missing data will include analysis of reasons for missingness using multinomial logistic regression. Sensitivity analyses will include missing data imputation by predictive-matching algorithms and missing data exclusion under a missing-at-random assumption.

19 Human Subjects Protections

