### 5.2 Deep Phenotyping

A subset of patients (n=160) will undergo “deep” phenotyping, with additional testing such as quantitative sensory testing (QST), functional neuroimaging (fMRI), autonomic nervous system (ANS) function assessment, and collecting additional blood samples for basal and stimulated immune markers. While screening, recruitment, baseline visits, and light phenotyping visits will occur at the Back & Pain Center, study visits for deep phenotyping will take place at the Chronic Pain and Fatigue Research Center (CPFRC). The neuroimaging will take place off site at a UM-affiliated location. There will be two deep phenotyping assessments that take place at the CPFRC before and after the first

treatment.

Figure 2 SMART Study Diagram Including Assessment Strategy

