# Statistical Analysis Plan

Table 1 Schedule of Assessments

	Scheduled												Unscheduled Visits					
	Pre-screening (-30days)	Study Visit T1 (Week 1)	Ecological Momentary Activity (EMA)-1 (Week 1)	Study Visit T2 (Week 6)	Deep Visit 1 * (Week 6)	Ecological Momentary Activity (EMA)-2 (Week 6)	Intervention 1 (Weeks 7-14)	Study Visit T3 (Week 15)	Deep Visit 2 * (Week 15)	Ecological Momentary Activity (EMA)-3 (Week 15)	Intervention 2 (Weeks 116-23)	Study Visit T4 (Week 224)	Ecological Momentary Activity (EMA)-4 (Week 24)	Ecological Momentary Activity (EMA)-5 (Week 36)	Study Visit T5 (Week 36)	10 Mini-assessments (Weeks 3, 8, 10, 17, 21, 26, 28, 30, 32, 34)	1 Expanded Mini-assessment (Week 12)	1 Mediation Mini-assessment (Week 19)
EMR Eligibility Review	x																	
Screening Eligibility Review	x	x																
Informed Consent		x																
Charlson Comorbidity Index (CCI)		x																
Demographics	x																	
Medical History and Medications	x		x				x				x			x				
Vitals, Height & Weight	x		x				x			x			x					
Biomechanical, Physical Exam & Physical Function Measures																		
2-Minute Walk Test (2MWT)		x		x			x			x		x		x				
4-Meter Walk Gait Speed Test (from SPPB)																		
Timed Sit-to-Stand (STS)																		

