### 9.3 Objective 3 Analysis Plan

**Objective 3:** Identify the mechanisms that explain the causal treatment effects.

The primary analysis for the exploratory objective 3 (specific aim 2) will involve a series of mediation analyses in order to identify the mechanisms that underlie the differential treatment responses. This analysis will use light phenotyping data from T2 and the interim assessment conducted at the midpoint of the first-stage treatment period. Second-treatment stage data will not be used for this analysis. Investigators did not propose a light phenotyping-based mediator for the Duloxetine treatment. Thus, a mediation analysis based on light-phenotyping data will not be carried out for this study arm.

The study does not include a control group since each of the four therapies have been previously shown to be effective for treating cLBP. As a result, the mediation analyses will be conducted by treatment group. Within each treatment group, the proposed treatment modifier will play the role of the exposure in the mediation analysis. Hypothesized mediators were determined by the study investigators and are listed in Table 6 by treatment arm.

For example, consider the PT/Exercise treatment group. Investigators expect that individuals who both receive the PT/Exercise treatment and have lower self-perception of their own efficacy will respond better to the PT/Exercise intervention and have lower PROMIS Pain Interference scores at follow up. They believe that this effect is attributable in part to changes in the patients fear avoidance beliefs and avoidance behaviors. The mediation analysis will assess whether greater pain catastrophizing is associated with a greater reduction in fear avoidance beliefs, which leads to greater improvement in pain interference scores.

The outcome measure for each mediation analysis will be the PROMIS Pain Interference score measured at T3. The exposures and mediators will be measured at T2 and the first treatment-stage midpoint, respectively.

*Table 6 Hypothesized Mediation Analyses by Treatment.*

Treatment	Mediation Analysis Exposure (X)	Expected treatment mediator (M)
MBSR	PROMIS Pain Catastrophizing	Experiences Questionnaire Score
PT/Exercise	Pain Self-Efficacy Score	Fear Avoidance Beliefs Questionnaire
Acupressure	Fibromyalgia Screening Score	GSS-8

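### The exploratory mediation test for deep biomarkers cannot establish mediation of the T2–T3 treatment effect, because no scheduled deep measure falls between treatment start and T3

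*Protocol*

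**What the plan says.** **The test.** In the causal-analysis paragraph of Protocol 18.1.5, a deep biomarker is added to the regression of outcome on treatment. The PTE is the relative change in the treatment coefficient. A Wald statistic (that change divided by its bootstrap standard error) "will be used to test for the presence of the mediation effect". Section 18.2.2 repeats the method for QST, inflammatory and fMRI markers, with "Wald tests to evaluate the mechanistic (mediation) effect". Neither section says which visit's biomarker value enters the model. Neither states an assumption about time order or plans a check on direction.

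**The timing.** Protocol Section 10 on the deep visits: "There will be two visits that take place after T2-before Treatment 1 and after T3-before Treatment 2". SAP 5.2 agrees ("There will be two deep phenotyping assessments that take place at the CPFRC before and after the first" treatment). SAP Table 1 puts T3 and Deep Visit 2 in the same nominal week, week 15. The primary endpoint is the change in PROMIS Pain Interference from T2 to T3 (Protocol 1.1, SAP 4.3).

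**The contrast.** For light measures, SAP 9.3 orders the variables in time: "The exposures and mediators will be measured at T2 and the first treatment-stage midpoint, respectively", with the outcome at T3. The SAP gives no deep mediation model, although its Tables 3 and 5 label vagal tone a mediator.

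**The concern.** A mediator of a randomized treatment effect has to be changed by the treatment and has to act before the outcome is recorded. A Deep Visit 1 value fails the first condition. A Deep Visit 2 value fails the second, or at best is concurrent with the outcome. Yet the protocol attaches a significance test for mediation to this design.

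The opposite direction is plausible for at least some of the markers. Protocol 10.2 provokes back pain and then rescans: resting connectivity and spectroscopy scans "will be repeated to assess the neurobiological response to increases in pain". The investigators therefore expect pain to move these signals.

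What is at stake is the mechanistic reading. Section 18 wants to place factors on a causal pathway to the benefit of a specific treatment, and Aim 3 includes inferring mechanisms of action. A marker that merely follows pain relief could be reported as the mechanism of that relief.

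**Working it through.** **1. The plan's own figures.** No power or error rate is given for the mediation test. The nearest stated figures are for the correlation test in 18.1.5. With the Fisher z approximation, power = Φ(atanh(r)·√(n−3) − 1.96):
- n = 40, r = 0.43: 0.4599 × 6.083 − 1.96 = 0.838, so 79.9% (80.8% with the bias term r/(2(n−1))). Stated: 81%.
- n = 100, r = 0.30: 0.3095 × 9.849 − 1.96 = 1.088, so 86.2%. Stated: at least 86%.

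Both reproduce, so n = 40 per treatment is a fair basis for what follows.

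**2. Inputs.**
- From the documents: 40 per arm (18.1.5).
- Carried over: the two-sided 5% level, stated there for the correlation test.
- Assumed: rho, the within-arm correlation of marker and pain change. I use 0.30, 0.43 and 0.51 because the power section uses them, but there they describe other correlations.
- Assumed: d, the difference between two arms in pain change, at 0.3, 0.5 and 0.8 SD. The documents give no between-arm difference.

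**3. PTE when pain drives the marker.** Let A be the arm (0 or 1), Y = dA + u, and M = rho·Y + √(1−rho²)·e, with u and e independent standard normal. Treatment reaches M only through Y, so mediation by M is zero.
- Unadjusted treatment coefficient: d.
- Within-arm slope of Y on M: rho. Arm difference in M: rho·d.
- Adjusted coefficient: d − rho·(rho·d) = d(1 − rho²).
- PTE = [d − d(1 − rho²)]/d = rho², whatever d is.

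So 0.30² = 9%, 0.43² = 18.5% and 0.51² = 26%.

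**4. Why the test cannot see direction.** Now take partial true mediation: M = rho·d·A + e and Y = d(1 − rho²)A + rho·M + √(1−rho²)·u. The arm difference in Y is d(1 − rho²) + rho·(rho·d) = d, the arm difference in M is rho·d, both within-arm variances are 1, and their correlation is rho. This is the same joint distribution as in step 3. No statistic computed from A, Y and M alone can separate the two.

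**5. Rejection rates.** The Wald test was simulated with 40 per arm and 400 bootstrap resamples (2,000 trials for the reverse path, 1,000 for true mediation):

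| d (SD) | rho | Pain drives marker | True mediation |
|---|---|---|---|
| 0.3 | 0.30 | 1.8% | 1.5% |
| 0.3 | 0.43 | 5.2% | 5.9% |
| 0.3 | 0.51 | 8.2% | 7.1% |
| 0.5 | 0.30 | 2.8% | 2.5% |
| 0.5 | 0.43 | 10.4% | 9.7% |
| 0.5 | 0.51 | 17.6% | 16.5% |
| 0.8 | 0.30 | 3.8% | 5.2% |
| 0.8 | 0.43 | 23.1% | 24.4% |
| 0.8 | 0.51 | 36.8% | 37.1% |

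By step 4 the last two columns estimate the same quantity, so their differences are simulation error.

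**6. Deep Visit 1 value instead.** For a marker measured before randomization the expected change in the coefficient is zero. Simulated: −0.4% to +1.3% of the effect, with rejection in 0.7% to 3.6% of trials. The direction problem goes away, but so does any chance of showing mediation of the treatment effect.

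**The case against.** Several points against this have force.

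- **It is exploratory.** Protocol 18.1 and the causal paragraph say so, and 10.2.1 says treatment mechanism is not the main objective of Aim 3. The SAP labels 14 of its 15 deep variables moderators and specifies no deep PTE test. This stands and limits the impact. It does not turn a test that is blind to direction into a test of mediation.
- **A false positive is far from certain.** A reader might infer that the trial will declare mediation. The table does not support that: where d or rho is small, rejection is below 5%. All four arms are active, and the only effect size in the documents for any arm (0.3 to 0.5 for mindfulness, Protocol 2.2.1) is not a between-arm difference, so 0.8 SD is a generous upper case. What does not depend on d is the spurious PTE estimate.
- **Section 10.2 is narrow evidence.** It concerns resting connectivity and spectroscopy after acute provocation. It does not show that eight-week change in pain interference moves QST, cytokines or gene expression. The reverse path is plausible for some markers and unproven for the rest.
- **Deep Visit 1 values may have a legitimate role.** 18.1.5 also speaks of deep markers mediating the effects of light phenotypes. A chain from T1 light phenotype to Deep Visit 1 marker to T3 outcome is correctly ordered. The PTE, however, is defined on treatment coefficients, and for those a Deep Visit 1 value cannot mediate.
- **The SAP drops nothing.** One might read SAP 9.3 as a timing rule abandoned for deep data. It covers light measures only and is silent on deep mediation.

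The unscheduled deep visit (Protocol 10.4) does not fill the gap: it is offered only before a non-study procedure, to a self-selected few.

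**Conclusion.** The concern holds as a limit on what the test can conclude. No scheduled deep measure lies between treatment start and T3, so the PTE and its Wald test in 18.1.5 and 18.2.2 cannot establish that a deep biomarker mediates the T2–T3 treatment effect. With the Deep Visit 2 value, a marker that only follows pain yields an expected PTE of rho squared (9% to 26% for rho 0.30 to 0.51). The test then rejects in roughly 2% to 37% of trials at 40 per arm and d of 0.3 to 0.8 SD, as often as under true mediation of the same size. The values of rho and d, the two-arm comparison and normality are assumptions. The timing gap and the equivalence of the two directions do not depend on the values chosen for rho and d. The primary analysis is unaffected.

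**What to change.** In Protocol 18.1.5 and 18.2.2:

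1. State that the Deep Visit 2 value, or the change from Deep Visit 1 to Deep Visit 2, is the biomarker measure used.
2. Report the PTE and its test as a concurrent association, and remove the wording that it tests for mediation.
3. Show beside it the reversed model, with the biomarker as outcome and T3 pain interference as the intermediate. This does not settle direction; it shows readers how well the alternative fits. Under the model in step 3 of the working, the treatment coefficient for the marker falls from rho·d to rho·d − rho·d = 0.
4. Do not use Deep Visit 1 values as mediators of the randomized treatment effect. They may still be studied as moderators, or as intermediates of a T1 light phenotype.
5. Limit mediation claims to measures taken between treatment start and T3, as SAP 9.3 plans for its light mediators.

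A lagged model (Deep Visit 2 marker against week 17 or T4 pain, adjusted for T3 pain) should not be offered as a mediation test. T3 pain lies on the path under study. If later pain follows from T3 pain, then given T3 pain neither treatment nor marker has anything left to explain; simulations under that assumption detected true mediation in at most 6% of trials. It also addresses pain during or after Treatment 2.

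Cost: wording and one extra model on data already planned, with no new visits. The price is a weaker mechanistic claim from the deep data.

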18.1.5 Descriptive statistics

We will use descriptive statistics to assess data quality and characterize relationships between phenotype features prior to each treatment. In preparation for the main multivariate model-based analysis we will look at correlations between phenotype variables and responses with correlation analysis and scatterplots, analyze data for evidence of (near) collinearity between factors, study patterns of missing data, and conduct univariate analysis using models described below. The goal of this analysis is to elicit a good feel for the specific data in our team of analysts and to guide an initial approach to data reduction and predictive model trimming. Another round of descriptive model-based analysis will occur after the multivariate model-based data analysis to assess the adequacy of proposed models with model diagnostic plots and other tools.

Longitudinal data analysis. For hypothesis testing, we will use model-based likelihood ratio tests. The main hypotheses of differential treatment effects (treatment moderators, treatment effect modifiers) will be handled by introduction of the interaction terms between the phenotype and treatment indicator variables. We will base longitudinal analysis on multivariate linear and logistic mixed models with choice appropriate to the type of response variable (Logistic regression with yes/no type variables; the Proportional Odds Cumulative Logit for modeling ordinal responses; linear model and generalized linear model with continuous quantitative scores). Gaussian subject-specific intercept term will be used to model the effect of unmeasured factors shared by longitudinal observations on the same subject. While the continuous form of analgesic and secondary endpoint variables will be used in the primary line of analysis, for robustness and to gain insight into a need for specific link functions and variable transformations, we will also use binary (clinically relevant 30% and 50% improvement in analgesic responses [yes/no]) as well as ordinal form of the responses.

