Handling protocol deviations. Participant-specific protocol deviations will be assessed for their potential relationship to the treatment effects or the course of the disease by a medical expert. Since deviations because of safety will generally result in incomplete data on the subject, their consequences will be handled in the analysis as potentially informative missing data (as described above). Because of the difficulty of accurate determination of the relationship between protocol deviations and the treatment efficacy and the disease dynamics, several versions of the primary and secondary analysis will be undertaken:

Exclusion of the violators from the analysis population under the missing at random assumption.

1. Single (if, as expected, missing data fraction does not exceed 15%) or multiple imputation of the violator's unobserved responses using predictive matching algorithms, including the per-protocol analysis of the resultant imputed population(s).
2. With yes/no responses that have the meaning of success or failure where mixed logistic models are used per protocol, violator's responses will be classified as failures for the conservative analysis.
3. Analytic methods (2,3) applied only to violators classified as treatment or disease-related as defined by medical experts.

Power for explaining treatment effects. Consider a regression model correlating within-patient improvement due to one of the 4 main treatments with a phenotypic variable. Using a two-sided test for correlation at 5% significance level we conclude that we will have the power of at least 86% to detect correlation of 0.3 or higher, conservatively assuming the model is applied to one randomized treatment segment with 100 patients. This corresponds to first phase or second phase treatment in one of the 4 treatment groups, and a model based on the light phenotyping patient group of 400 total. Similar analysis for the smaller subgroup based on 40 patients with available deep phenotyping for a specific treatment and segment shows that correlation of 0.43 or higher will be detectable with 81% power. This is well within reach as evidenced by available literature on the association between treatment effects and phenotype variables. For example, mindfulness and pain responses showed correlations of 0.43-0.51 in prior reported studies. Our previous studies of the association between pain centralization and analgesic responses in knee OA showed similar or higher correlations.

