22.2 Participant Discontinuation

Participants may withdraw voluntarily from the study or the PI may discontinue—a participant from the study. In some cases, a participant may withdraw from the study intervention—or be discontinued from the study intervention by the PI(s)—and still continue to participate in other aspects of the study. If the participant no longer meets the inclusion/exclusion criteria for the study, they may be withdrawn. For example, the participant becomes pregnant or is diagnosed with cancer.

If a participant chooses to withdraw from an intervention and they can still continue participation in the study. They will be asked to come in for the remaining study visits and complete the mini-assessments.

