## Statistical Analysis Plan

the intent-to-treat framework using the treatment assigned to each subject instead of the treatment that each subject may have actually received.

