### 8.3 Protocol Deviations

An accidental or unintentional change to, or non-compliance with the research protocol that does not increase risk or decrease benefit or; does not have a significant effect on the subject's rights, safety, or welfare; and/or on the integrity of the data. Deviations may result from the action of the subject, researcher, or research staff's departure from the IRB approved research protocol without prior IRB approval for the variation. Missing data are part of protocol deviations and may lead to exclusion from the per-protocol analysis population.

Participant-specific protocol deviations will be assessed for their potential relationship to the treatment effects or the course of the disease by a medical expert. Since deviations because of safety will generally result in incomplete data on the subject, their consequences will be handled in the analysis as potentially informative missing data (see Section 8.4). Due to the difficulty of accurate determination of the relationship between protocol deviations and the treatment efficacy and the disease dynamics, several versions of the primary and secondary analysis will be undertaken:

1. Exclusion of the violators from the analysis population under the missing at random assumption.
2. If missing data fraction exceeds 15%, multiple imputation of the violator's unobserved responses using predictive matching algorithms, including the per-protocol analysis of the resultant imputed population(s).
3. With yes/no responses that have the meaning of success or failure where mixed logistic models are used per protocol, violator's responses will be classified as failures for the conservative analysis.
4. Analytic methods (2,3) applied only to violators classified as treatment or disease-related as defined by medical experts.

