### 8.5 Treatment Compliance

Treatment compliance for each of the four study treatments is defined below in Table 4.  
*Table 4 Compliance standards for treatments*

Treatment	Compliance Standard
MBSR	Completion of 4 out of 8 sessions
PT/Exercise	Completion of 80% of PT sessions

Acupressure	Completion of 70% of the 30-minute sessions.
Duloxetine	Compliance will be assessed by counting pills returned to research pharmacy.

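### Setting protocol violators' yes/no responses to failure is not conservative for comparing four active arms, and the rule as written can overwrite observed responders

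*Protocol*

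**What the plan says.** Because the effect of deviations is hard to judge, Protocol 18.1.5 (paragraph on handling protocol deviations) states that "several versions of the primary and secondary analysis will be undertaken". In one of them a "violator's responses will be classified as failures for the conservative analysis". SAP 8.3 repeats this as item 3, with the scope "With yes/no responses that have the meaning of success or failure where mixed logistic models are used per protocol". The preceding item in each list imputes only the violator's unobserved responses. The failure item carries no such limit.

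Other places bear on the rule:

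- Protocol 22.2 lets participants who leave an intervention stay in the study: "They will be asked to come in for the remaining study visits and complete the mini-assessments".
- SAP 5.1 says there is no control group, because the four treatments are taken as already shown to work.
- SAP Table 4 (section 8.5) sets the compliance standards. MBSR is "Completion of 4 out of 8 sessions", PT is "Completion of 80% of PT sessions" and acupressure is 70% of sessions. Duloxetine has a pill count with no threshold. The SAP uses these standards to define the per-protocol population (7.2.2, 8.1).
- SAP 8.3 defines deviations broadly, to include non-compliance with the protocol and missing data.
- On priority, Protocol 18.1.5 says: "While the continuous form of analgesic and secondary endpoint variables will be used in the primary line of analysis". The binary 30% and 50% improvement forms are added for robustness. SAP 7.2.1 puts the primary analysis under intent to treat, "using the treatment assigned to each subject instead of the treatment that each subject may have actually received".

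**The concern.** Coding dropouts or violators as failures earns the name conservative in a single arm, where it gives a lower bound on response, or where it works against a new treatment compared with a control. Here every arm is active and the question is which treatment suits which patient. Lowering one arm's response raises the apparent standing of the others, so no direction is cautious.

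Two features add to this. The rule covers responses in general, so a participant who left the intervention, attended T3 and met the 50% improvement criterion would be analysed as a failure. And if non-compliance counts as a violation, the bar differs by arm: half the sessions in MBSR and 80% in PT. Equal attendance would then produce unequal recoding. A reader who sees the label would trust this version most when it disagrees with the others.

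**Working it through.** **Plan's own figure.** The plan gives no figure for this rule. The nearest stated figure, in the same section, is at least 86% power for a correlation of 0.3 with 100 patients. The Fisher z formula gives Φ(atanh(0.30)·√97 − 1.96) = Φ(0.3095 × 9.849 − 1.96) = Φ(1.088) = 0.862, so it reproduces.

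**Inputs from the documents.** True response is 30% in each arm (Protocol 18.1.5, power for prediction, for 50% improvement). There are 102 patients per arm (SAP 6) and tests are two-sided at 5%. MBSR needs 4 of 8 sessions, PT 8 of 10 (80% of the 10 sessions in Protocol 9.2), and acupressure 40 of 56 days (70% of daily use for 8 weeks).

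**Assumptions.** Failing Table 4 makes a violator. Attendance is the same in every arm, with mean 70%, 80% or 90% and intraclass correlation (ICC) between patients of 0 to 0.3. Violation is unrelated to response.

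**Arm difference.**

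1. Violation rate v: P(X ≤ 3 of 8) for MBSR and P(X ≤ 7 of 10) for PT, binomial at ICC 0 and beta-binomial otherwise.
2. Recoded response: 0.30 × (1 − v).
3. Rejection rate: Φ((d − 1.96·SE0)/SE1) plus the opposite tail, where d is the difference, SE0 the pooled and SE1 the unpooled standard error.

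At mean 80% and ICC 0, v = 0.010 and 0.322. Response becomes 0.297 and 0.203, so d = 0.094, SE0 = 0.0606 and SE1 = 0.0603. The rejection rate is 34%. At ICC 0.3, v = 0.112 and 0.315, response is 0.267 and 0.205, and rejection is 18%.

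| Mean attendance | Violators, MBSR | Violators, PT | MBSR v PT rejection, ICC 0–0.3 | PT v acupressure rejection, ICC 0.1–0.3 |
|---|---|---|---|---|
| 70% | 6–20% | 48–62% | 31–86% | 6–8% |
| 80% | 1–11% | 32–33% | 18–34% | 6–9% |
| 90% | 0–4% | 7–15% | 6–9% | 5–6% |

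The upper ends at 70% and 80% need ICC 0, meaning no variation between patients in attendance. At ICC 0.3 they fall to 31% and 18%.

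**Hiding a difference.** The recoded PT-to-MBSR response ratio is the true ratio times (1 − 0.315)/(1 − 0.112) = 0.77 at 80% and ICC 0.3. A true PT advantage with a ratio of 1/0.77 = 1.30 would vanish.

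**Moderators.** These are simulations of four arms of 102, with a logistic model for arm, phenotype and PT-by-phenotype, no true effect, and rejection at |W| ≥ 2 as in SAP 9.1.1.

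| Pattern of violation | PT-by-phenotype rejection |
|---|---|
| Observed responses, not recoded | about 4–6% |
| Unrelated to phenotype, equal or unequal rates by arm | 4–5% |
| Odds ratio 2 per SD in every arm | 4–6% |
| Odds ratio 3 per SD in every arm, 40% violators in PT | 9% |
| Odds ratio 2 per SD in PT only, 20% to 40% violators in PT | 9–15% |
| Rising 10% to 40% from −1 to +1 SD in the other three arms, flat 20% in PT | about 14–15%, coefficient about +0.26 |
| Mirror of the row above | about 12–13%, coefficient about −0.26 |

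A false moderator needs a phenotype whose relation to the probability of violation differs by arm. Unequal cut-offs alone do not produce one.

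**The case against.** The case against has real force. The rule touches only binary outcomes in logistic models, and SAP section 9 specifies neither a binary endpoint nor a logistic model. It is one of several listed versions, alongside exclusion, imputation of unobserved responses, and restriction to violators judged treatment- or disease-related. Table 4 is tied to the per-protocol population, not to the word violator. The documents give no attendance data, MBSR against PT is the widest pair of numeric cut-offs, and the SAP plans no test of equal response between those two arms. All of this stands, and it limits the size of the point. It does not make the label right for a comparison between arms.

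A reader might infer three stronger things that the documents do not support:

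- *That the rule breaks intent to treat.* SAP 7.2.1 concerns treatment assigned against treatment received, in the primary analysis. Failure coding leaves each patient in the assigned arm and changes the outcome, and a sensitivity version may do that.
- *That the Table 4 cut-offs generate false moderators.* The simulations show nominal rejection unless phenotype predicts violation differently by arm. That is plausible, for instance for fear avoidance in PT, but no document says so.
- *That the rule was meant for missing data only, so no observed response is at risk.* The surrounding text is about incomplete data. But the preceding item says unobserved and this one does not, and Protocol 22.2 ensures that observed outcomes will exist.

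**Conclusion.** The point holds for one sensitivity version of the yes/no analyses. As written, the rule can overwrite observed responses. For comparing four active arms it is not conservative: it can create or hide an arm difference wherever violation rates differ, and a moderator only where a phenotype predicts violation differently by arm.

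The size depends on assumptions that the documents do not supply. If Table 4 defines violators and attendance is the same in both arms, false rejection for MBSR against PT is 18–34% at 80% attendance, with a range from near nominal (6–9% at 90%) to large (31–86% at 70%). PT against acupressure stays near nominal at ICC 0.1 to 0.3. Duloxetine cannot be computed, because Table 4 gives it no threshold. Protocol 9.4 lets participants stay at the lower dose or stop the medication, and whether they then count as violators is undefined. Those passages must be reconciled.

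The primary continuous intent-to-treat analysis of PROMIS Pain Interference is not affected. The change should still be made, because a stated rule and its label would mislead and correcting them costs little.

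**What to change.** In Protocol 18.1.5 and SAP 8.3:

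1. For binary responses, analyse violators' observed responses in their assigned arm and multiply impute only responses that are missing.
2. Delete the word conservative.
3. If the failure-coded version is kept, call it a composite of response and adherence. State who counts as a violator in each arm, including duloxetine. Report the number recoded by arm, and preferably by the hypothesized moderators.
4. Pair it with a version that varies the imputed responses in both directions, so that the reader sees how far each arm's result can move.

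The cost is wording in two documents and one extra table, with no new data. The downside is the loss of one convenient sensitivity label.
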